#### **5.1.7.2. Dose Modification of Cetuximab**

Prior to first and all subsequent infusions of cetuximab, subjects must receive premedication with an antihistamine and a corticosteroid at least 1 hour prior to administration of cetuximab (please see package insert for further information). Severe infusion-related reactions, including anaphylactic reactions, may commonly occur, in some cases with fatal outcome. Occurrence of a severe infusion-related reaction requires immediate and permanent discontinuation of cetuximab therapy and may necessitate emergency treatment. Some of these reactions may be anaphylactic or anaphylactoid in nature, accompanied by bronchospasms or urticaria, or represent a cytokine release syndrome. Symptoms may occur during the first infusion and for up to several hours afterwards, or with subsequent infusions. They can occur despite the use of premedication. It is recommended to warn subjects of the possibility of such a late onset and instruct them to contact their physician if symptoms or signs of an infusion-related reaction occur.

If during the first infusion, infusion-related reaction occurs within the first 15 minutes, the infusion should be stopped. If an infusion-related reaction develops later during the infusion or at a subsequent infusion, further management will depend on its severity:

- Grade 1: continue slow infusion under close supervision
- Grade 2: continue slow infusion and immediately administer treatment for symptoms
- Grade 3 and 4: stop infusion immediately, treat symptoms vigorously, and contraindicate further use of cetuximab

Mild or moderate infusion-related reactions are very common, comprising symptoms such as fever, chills, dizziness, or dyspnea that occur in a close temporal relationship, mainly to the first cetuximab infusion. If the subject experiences a mild or moderate infusion-related reaction, the infusion rate may be decreased. It is recommended to maintain this lower infusion rate in all subsequent infusions.

Additionally, cetuximab must be immediately discontinued in case of:

- Grade 3 or 4 infusion-related reaction related to cetuximab

- Occurrence of a second infusion-related reaction, following administration of cetuximab at a slower infusion rate.
- A fourth occurrence of Grade 3 skin reactions, despite appropriate dose reductions
- Occurrence of Grade 4 skin reactions

A close monitoring of subjects, particularly during the first administration, is required. Special attention is recommended for subjects with reduced performance status and pre-existing cardiopulmonary disease.

When cetuximab is administered with platinum-based chemotherapy, the frequency of severe leukopenia or severe neutropenia may be increased and thus may lead to a higher rate of infectious complications such as febrile neutropenia, pneumonia, and sepsis compared to platinum-based chemotherapy alone.

If a subject develops an intercurrent illness (eg, infection) that, in the opinion of the Investigator and/or the Sponsor, mandates interruption of therapy, this intercurrent illness must resolve within a time frame such that no more than 2 consecutive cetuximab infusions are withheld.

When cetuximab is administered in combination with chemotherapeutic agents such as cisplatin or carboplatin, refer to their respective product information. Chemotherapy must not be administered earlier than 1 hour after the end of the cetuximab infusion.

Cetuximab therapy will not be delayed for cisplatin-related toxicity. Therefore, if the next infusion of cisplatin is delayed, the subject will continue to receive weekly infusions of cetuximab. In case of cetuximab-related toxicity, cisplatin will not be delayed and the planned schedule for administration should be maintained. If the cetuximab therapy is terminated for cetuximab-related toxicity, cisplatin will be continued. If there is cetuximab-related toxicity that does not resolve to Grade 0 or 1 (or baseline grade if higher than Grade 1), cetuximab will be discontinued at the discretion of the investigator.

Dose modifications for cetuximab are described in Table 5.3 and [Table 5.4](#).

**Table 5.3: Cetuximab Dose Modifications**

Toxicity	Dose Reduction	Discontinuation
Infusion reaction	Reduce infusion rate by 50% for CTCAE Grade 1 or 2 and non-serious CTCAE Grade 3 infusion reaction	Immediately interrupt and permanently discontinue cetuximab infusion for serious infusion reactions

CTCAE = Common Terminology Criteria for Adverse Events.

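### Protocol 5.1.7.2 contradicts its own Tables 5.3 and 5.4 on stopping cetuximab for a non-serious Grade 3 infusion reaction and for Grade 4 acneiform rash, and Table 5.3 omits two further stop rules

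*Protocol*

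**What the plan says.** The text of Protocol 5.1.7.2 manages infusion reactions by severity. At the top of the scale it says "Grade 3 and 4: stop infusion immediately, treat symptoms vigorously, and contraindicate further use of cetuximab". A separate list of events for which cetuximab must be stopped at once repeats this: "Grade 3 or 4 infusion-related reaction related to cetuximab". The same list adds "Occurrence of a second infusion-related reaction, following administration of cetuximab at a slower infusion rate". For skin toxicity the list has two entries: the first is "A fourth occurrence of Grade 3 skin reactions, despite appropriate dose reductions", and the other is "Occurrence of Grade 4 skin reactions". Ahead of the severity scale stands a timing rule: "If during the first infusion, infusion-related reaction occurs within the first 15 minutes, the infusion should be stopped".

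The section then refers the reader to Tables 5.3 and 5.4 for cetuximab dose modifications. Table 5.3 has one row, for infusion reactions. Its rate-reduction cell reads "Reduce infusion rate by 50% for CTCAE Grade 1 or 2 and non-serious CTCAE Grade 3 infusion reaction"; its discontinuation cell covers serious reactions only. Table 5.4 is headed for severe acneiform rash of Grade 3 or 4. For the first three occurrences it delays the infusion by 1 to 2 weeks and, on improvement, gives 250, 200 and 150 mg/m² in turn. It ends cetuximab at the fourth occurrence, if there is no improvement, or if the delay exceeds 2 weeks.

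**The concern.** A site that works from the tables would keep cetuximab going, or bring it back, in a patient whom the text says to stop. A site that works from the text would stop the same patient. The protocol does not treat these events as remote. It warns: "Severe infusion-related reactions, including anaphylactic reactions, may commonly occur, in some cases with fatal outcome". In both contradictions the more permissive instruction is the one in the table, which is where the section sends the reader and what staff are likely to consult at the bedside.

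The stake is patient safety and uniform conduct in both arms. There is also a compliance question. Protocol 6.4 allows no deviation except to remove an immediate hazard, so monitors need to know which of two conflicting actions is the compliant one.

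**Working it through.** No arithmetic applies: no alpha, power, sample size or event count is involved. The check sets the text of 5.1.7.2 beside the tables, situation by situation, and asks whether one action satisfies both.

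| Situation | Text of 5.1.7.2 | Table | Can both be obeyed? |
|---|---|---|---|
| Non-serious Grade 3 infusion reaction | Stop; no further cetuximab | 5.3: halve the rate | No |
| Grade 4 acneiform rash, occurrences 1 to 3, improving within 2 weeks | Discontinue | 5.4: resume at 250, 200, 150 mg/m² | No |
| Second reaction at the slower rate (Grade 1–2) | Discontinue | 5.3: silent on recurrence | Yes, reading the text as an exception |
| Reaction in first 15 minutes of first infusion (Grade 1–2) | Stop the infusion; permanence not stated | 5.3: silent on timing | Yes, reading the text as an exception |
| First non-serious Grade 1–2 reaction, later than that | Slow | 5.3: slow | Yes, they agree |
| Serious Grade 3 or 4 reaction | Stop | 5.3: stop | Yes, they agree |
| Non-serious Grade 4 reaction | Stop | 5.3: no cell applies | Yes |
| Grade 3 acneiform rash, fourth occurrence | Discontinue | 5.4: discontinue | Yes, they agree |

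**First contradiction.** It could be defined away only if a Grade 3 reaction were always serious. Protocol 9.4.3 rules that out. It grades severity separately from seriousness and says that even a Grade 4 event may not be serious. The same section labels Grade 3 as severe, and 5.1.7.2 separately requires immediate and permanent discontinuation for a severe infusion reaction. The text therefore reaches the stop by three routes, while Table 5.3 keeps the patient on drug.

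**Second contradiction.** For Grade 4 acneiform rash the text allows 0 resumptions. Table 5.4 allows at most 3 (one each at 250, 200 and 150 mg/m²), each conditional on improvement and on a delay of no more than 2 weeks. The word permanent is not attached to the skin entries in the list. However, the fourth Grade 3 occurrence sits in the same list, and there Table 5.4 ends treatment, so discontinuation is naturally read the same way for Grade 4.

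**The two omissions.** The Grade 1–2 rate-reduction cell in Table 5.3 carries no limit on timing or recurrence. Someone using the table alone would slow the infusion where the text stops it. Someone using both would apply the text as the specific exception.

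**Search for a precedence rule.** Protocol 5.1.7 points to the prescribing information, to investigator discretion to reduce or withhold, and to optional contact with the medical monitor. The end of 5.1.7.2 points to the tables. Neither ranks text against tables. Precedence statements found: 0.

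**The case against.** The strongest reply is that the text already wins. It uses mandatory language, whereas Section 5.1.7 and Table 5.4 are both titled as guidelines, and the general section speaks of recommendations. That does favour the stricter reading, and it would be too strong to say that nothing indicates which action is the deviation. But Table 5.3 is not titled as a guideline, and the section closes by directing readers to the tables. Discretion to reduce or withhold is not expressly discretion to continue where the text says stop. Optional contact with the monitor does not help much during an infusion reaction.

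A reader might infer that text and tables give opposite instructions in four situations, adding the second reaction and the first 15 minutes. The documents do not support that. Table 5.3 is silent on recurrence and timing. The text itself pairs an unlimited slow-infusion rule for Grades 1 and 2 with a specific stop for a second reaction. Stopping in the first 15 minutes is not stated to be permanent, so stopping and later restarting at half rate would satisfy both.

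Two further points might be taken as separate conflicts and are not. The cetuximab hold for rash or mucositis in 5.1.7.1 applies after patritumab has been held without resolution, and it does not displace the specific Grade 4 stop. A serious Grade 1–2 reaction falls in both cells of Table 5.3, but a permanent stop naturally supersedes slowing.

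**Conclusion.** The concern holds as two direct contradictions (non-serious Grade 3 infusion reaction; Grade 4 acneiform rash at occurrences 1 to 3) and two text rules missing from Table 5.3, with no stated precedence. It should be fixed on safety and conduct grounds.

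Its size in patients is unknown. The protocol describes severe infusion reactions as common and mild or moderate ones as very common, but gives no rates, and no frequency for Grade 4 rash.

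A reader might infer a threat to the primary comparison. The documents do not support that: cetuximab is background treatment in both blinded arms, PFS is analysed as randomised, and under Protocol 5.1.7 a subject who stops cetuximab continues patritumab or placebo.

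The contradictions follow from the wording alone. The direction of the correction rests on one assumption, that the mandatory text is what the sponsor meant. The documents do not say so.

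**What to change.** First have the sponsor confirm that the stricter text is intended. If the tables were meant instead, the text needs changing and the steps below reverse. Otherwise:

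- **Table 5.3, rate-reduction cell:** remove non-serious Grade 3, leaving Grades 1 and 2.
- **Table 5.3, discontinuation cell:** state any Grade 3 or 4 infusion reaction, or any serious one.
- **Table 5.3, additions:** add the 15-minute rule and the second-reaction rule. Say whether cetuximab may be restarted after a 15-minute stop, which neither text nor table says now.
- **Table 5.4:** restrict the heading to Grade 3 and add a row: Grade 4, any occurrence, discontinue cetuximab.
- **Section 5.1.7.1 (optional):** cross-refer the cetuximab hold for rash to 5.1.7.2.
- **Sites:** notify all sites of the change.

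The cost is a protocol clarification or amendment, a site letter and possibly slightly more cetuximab discontinuations. Those subjects stay in the study on patritumab or placebo, with platinum up to its 6-cycle maximum. The analysis and sample size do not change.

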**Table 5.4: Cetuximab Dose Modification Guidelines for Acneiform Rash**

Severe Acneiform Rash (Grade 3-4)	Cetuximab	Outcome	Cetuximab Dose Modification
1 st occurrence	Delay infusion 1-2 weeks*	Improvement	Continue at 250 mg/m 
		No improvement	Discontinue cetuximab
2 nd occurrence	Delay infusion 1-2 weeks*	Improvement	Reduce dose to 200 mg/m 
		No improvement	Discontinue cetuximab
3 rd occurrence	Delay infusion 1-2 weeks*	Improvement	Reduce dose to 150 mg/m 
		No improvement	Discontinue cetuximab
4 th occurrence	Discontinue		

\* If infusion is delayed >2 weeks, discontinue cetuximab treatment.

### 5.1.7.3. Dose Modification of Cisplatin

Repeating administration of cisplatin must be delayed until normal values are achieved (wait one cycle for recovery) for the following parameters:

- Serum creatinine < 1.5 mg/dL
- Urea < 25 mg/dL
- White blood cells > 4.0 x 10^9/L
- Blood platelets > 100 x 10^9/L
- Non-hematological cisplatin-related toxicities to resolve to ≤ Grade 1
- However, skin reactions, paronychia, fatigue, ototoxicity, or neurotoxicity should resolve to ≤ Grade 2

Please see package insert for further information.

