#### **5.1.7. Guidelines For Dose Modifications**

For those subjects who continue treatment, the Investigator will evaluate which hematological and/or non-hematological toxicities are attributed to which drug(s), and adjust the dose of one or more of the drugs as recommended below.

If a subject experiences an unacceptable toxicity to cisplatin, the Investigator will be able to withhold drug, reduce dose, or switch to carboplatin. If the Investigator chooses to start treatment with carboplatin, then carboplatin will be administered throughout the study. If a subject also experiences an unacceptable toxicity to carboplatin, then carboplatin treatment will be withheld or dose reduced.

Subjects with unacceptable toxic effects of one of the study drugs will receive only the tolerated drugs until disease progression.

- If patritumab/placebo needs to be discontinued, the subject will be withdrawn from the study
- In subjects whose cisplatin or carboplatin therapy is discontinued, reduced, or delayed, the patritumab and cetuximab will be continued and subjects will continue to undergo tumor assessments at 6 week intervals until disease progression or unacceptable toxicity
- In subjects whose cetuximab dose is discontinued, reduced, or delayed, the patritumab will be continued. Cisplatin or carboplatin will be administered for a maximum of 6 cycles
- In subjects whose cetuximab and cisplatin or carboplatin are either discontinued or delayed, patritumab will be continued as monotherapy

In addition to the recommendations provided below, please refer to the respective current prescribing information for detailed recommendations on managing suspected toxicities, for guidance on withholding, dose reductions, and discontinuation. If toxicities occur, it is up to the discretion of the Investigator to dose reduce or withhold one or more medications until recovery or resolution of the AE to Grade 0 or 1.

In individual cases, if a subject discontinues study drugs for an extended time period, the subject may restart study drugs at the discretion of the investigator after discussion with the Sponsor and CRO's medical monitors.

Investigators may contact the Sponsor's medical monitor to discuss any question regarding dose modification or discontinuation of study drugs.

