#### *Neuropathies*

Neuropathies may manifest by paresthesia, areflexia, and a proprioceptive loss of sensation of vibrations. A neurologic examination must be carried out at regular intervals.

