#### *Ototoxicity*

Ototoxicity has been observed in up to 31% of patients treated with a single dose of cisplatin 50 mg/m^2, and is manifested by tinnitus and/or hearing loss in the high frequency range (4000 to 8000 Hz).

*Allergic phenomena*

As with other platinum-based products, hypersensitivity reactions appearing in most cases during perfusion may occur, and necessitate discontinuation of the perfusion as an appropriate symptomatic treatment.

Anaphylactic-like reactions to cisplatin have been observed. These reactions can be controlled by administration of antihistamines, adrenaline, and/or glucocorticoids.

*Hepatic function and hematological status*

The hematological status and the hepatic function must be monitored at regular intervals.

*Injection site reactions*

Injection site reactions may occur during the administration of cisplatin. Given the possibility of extravasation, it is recommended to closely monitor the infusion site for possible infiltration during drug administration.

Special care is required for subjects with acute bacterial or viral infections.

Table 5.5 lists toxicities and related dose modifications and discontinuations.

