**Table 5.5: Cisplatin Dose Modifications and Discontinuations\* for Toxicities**

Toxicity	Dose Modification/Discontinuation
Hematological	A repeat course should not be given until circulating blood elements are at an acceptable level (ie, platelets $\geq 100 \times 10^9/L$ , white blood cells $\geq 4 \times 10^9/L$ )
Febrile neutropenia/infection	The first episode of febrile neutropenia or infection will result in reduction by 20% of cisplatin dose. If there is a second episode, despite dose reduction, the subject must receive prophylactic antibiotics during subsequent cycles. If there is a third episode, the subject will be withdrawn from study.
Neutropenia	Grade 2 or 3: cisplatin treatment delay until < Grade 1. Grade 4: cisplatin treatment delay until < Grade 1; dose reduction of all further doses of cisplatin by 20%.
Nephrotoxicity	A repeat course of cisplatin should not be given until the serum creatinine is below 1.5 mg/100 mL, and/or the urea is below 25 mg/100 mL
Thrombocytopenia	Grade 1: cisplatin treatment delay until platelets $\geq 100,000/mm^3$ . $\geq$ Grade 2: cisplatin treatment delay until platelets $>100,000/mm^3$ , dose reduction of all further doses of cisplatin by 20%

Toxicity	Dose Modification/Discontinuation
Organ Toxicity	Grade 2: Delay chemotherapy until $\leq$ Grade 1. $\geq$ Grade 3 or more: Delay chemotherapy until $\leq$ Grade 1; dose reduction of all further doses of cisplatin by 20%. Do not delay or reduce cisplatin dose if there are asymptomatic increases in transaminases, cetuximab-induced skin reactions, and subclinical side effects (e.g. nausea, vomiting, alopecia, altered taste).
Ototoxicity	Criteria for hearing testing
Neuropathy	In case of sensory neuropathy $\geq$ Grade 2, change cisplatin to carboplatin

Note: Please refer to the cisplatin package insert for additional information on potential toxicities and their management. When cisplatin is administered in combination with other agents such as cetuximab, refer to their respective product information. \*If events do not recover within 3 weeks, discontinue cisplatin treatment.

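### At Grade 2 sensory neuropathy, Protocol Section 5.1.7.3 permits repeat cisplatin while Table 5.5 requires carboplatin, and nothing says which rule governs

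*Protocol*

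**What the plan says.** Protocol Section 5.1.7.3 opens with a mandatory hold: "Repeating administration of cisplatin must be delayed until normal values are achieved (wait one cycle for recovery) for the following parameters". The list that follows has separate entries for creatinine below 1.5 mg/dL and urea below 25 mg/dL. It also has a general entry requiring non-hematological cisplatin toxicity to reach Grade 1 or lower. The last entry relaxes that standard for a named group: "However, skin reactions, paronychia, fatigue, ototoxicity, or neurotoxicity should resolve to" Grade 2 or lower.

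Later in the subsection the reader is told that "Table 5.5 lists toxicities and related dose modifications and discontinuations". The neuropathy row of that table covers sensory neuropathy at or above "Grade 2, change cisplatin to carboplatin". The nephrotoxicity row bars a repeat course until creatinine is below 1.5 mg/100 mL, "and/or the urea is below 25 mg/100 mL". A note under the table stops cisplatin for events that have not recovered in three weeks.

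Section 5.1.7 gives the general position. For unacceptable cisplatin toxicity "the Investigator will be able to withhold drug, reduce dose, or switch to carboplatin", and investigators may contact the sponsor's "medical monitor to discuss any question regarding dose modification or discontinuation of study drugs".

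**The concern.** The two rules sit in one subsection, concern the same drug and the same finding, and give opposite answers at Grade 2. A site working from the list re-doses cisplatin. A site working from the table takes the patient off it.

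Neuropathy is a known cisplatin toxicity, and the protocol expects it to be looked for: "A neurologic examination must be carried out at regular intervals". The rule will therefore be used. About 35 sites are planned, so uniform handling cannot be assumed where the text allows both actions.

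At stake is whether patients with the same finding are managed in the same way. Section 6.4 also requires the sponsor to be told of all deviations, including dosing deviations, and under two conflicting rules it is unclear whether re-dosing at Grade 2 is one.

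**Working it through.** The plan gives no figure to reproduce here, so the check is a side-by-side reading.

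**Neuropathy.** The inputs are the last entry of the Section 5.1.7.3 list, the neuropathy row of Table 5.5 and the note under that table.

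| Sensory neuropathy | Section 5.1.7.3 list | Table 5.5 row | Agree? |
|---|---|---|---|
| Grade 0 or 1 | Repeat allowed | No switch required | Yes |
| Grade 2 | Repeat allowed | Switch to carboplatin | No |
| Grade 3 or above | Hold; repeat allowed once at Grade 2 or lower | Switch to carboplatin | No, subject to the limit below |

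The limit on the last line comes from the documents. The list speaks of waiting one cycle, a cycle is 21 days (Section 3.1.5), and 21/7 = 3 weeks, which matches the note under Table 5.5. An event that stays above Grade 2 for three weeks ends cisplatin under either text. At Grade 3 or above the rules therefore lead to different treatment only when the event improves to Grade 2 or lower in that time.

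**Is there a precedence rule?** Four places could supply one.
- Section 5.1.7 offers withholding, reducing and switching as options. It also mentions recovery to Grade 0 or 1 as a further threshold. It does not rank the list against the table.
- The medical-monitor contact in Section 5.1.7 is optional.
- The pointer to Table 5.5 introduces the table without saying that it overrides the list.
- The references to the package insert, after the list and under the table, say nothing about which of the two prevails.

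None settles the Grade 2 case.

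**Creatinine and urea.** Since 100 mL = 1 dL, the limits are the same in both places: 1.5 mg/dL for creatinine and 25 mg/dL for urea. Only the connective differs.

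| Creatinine | Urea | List (both required) | Table, 'and' | Table, 'or' |
|---|---|---|---|---|
| below limit | below limit | repeat | repeat | repeat |
| not below | below (e.g. 1.6 and 20) | hold | hold | repeat |
| below | not below (e.g. 1.2 and 30) | hold | hold | repeat |
| not below | not below | hold | hold | hold |

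Read as 'and', the table matches the list in every case. A difference appears only under the 'or' reading, and only when one value has recovered and the other has not.

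**The case against.** The strongest reply is that the texts can be applied together. The list sets a minimum for re-dosing and does not order cisplatin once that minimum is met. The table row covers a narrower event, sensory neuropathy, so it can be taken as the specific rule and the list as the general one. A site applying the stricter rule item by item satisfies both. The section is framed as guidance, leaves room for investigator judgment and offers the medical monitor.

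Much of this stands. The specific-over-general reading is sensible, and the fix below adopts it. But the protocol does not state it. The list's exception names neurotoxicity outright, and the paragraph on neuropathies in the same subsection describes it largely by sensory signs such as paresthesia and loss of vibration sense. A reader of the exception would therefore naturally apply it to sensory neuropathy. The workaround also depends on each site noticing the conflict.

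Three stronger readings are tempting and are not supported.
- *The renal rules also contradict each other.* The cut-offs are identical, and the 'or' reading requires ignoring a mandatory list in the same subsection. This is an ambiguity to tidy.
- *The conflict is equally sharp at Grade 3 or above.* The three-week limit narrows it there.
- *The size can be given as cisplatin dose.* Before cycle 4, three planned doses remain, 3 x 100 = 300 mg/m2, available under the list and not under the table. That is an upper bound assuming full doses, no other hold and no rise in grade. It does not say how many patients are affected.

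**Conclusion.** The point holds for sensory neuropathy. At Grade 2 the protocol gives two opposite instructions and no rule for choosing between them. At Grade 3 or above there is a narrower difference, confined to events that improve to Grade 2 or lower within three weeks. The wording on creatinine and urea is a secondary clarification.

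The number of subjects affected cannot be computed. The documents give no expected rate of sensory neuropathy by grade or cycle, and the choice between cisplatin and carboplatin is left to the investigator.

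A reader might infer that the inconsistency threatens the trial's result. The documents do not support that. The same rules apply to both arms under blinding, and the platinum agent is not an input to the sample-size calculation. Power, alpha and the PFS comparison are unaffected. The issue is consistent patient safety management, and it deserves correction on that ground alone.

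The conclusion rests on reading the list's neurotoxicity entry as including sensory neuropathy, which is its ordinary meaning.

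**What to change.** In the last entry of the Section 5.1.7.3 list, after the Grade 2 allowance, add: *except sensory neuropathy of Grade 2 or above, for which change to carboplatin (Table 5.5)*. This resolves Grade 2 and the higher grades together and leaves the allowance in place for the other toxicities named there.

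As a secondary clarification, replace *and/or* with *and* in the nephrotoxicity row of Table 5.5, so that it matches the list's requirement for both values.

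The cost is a short protocol wording amendment, with the usual review, and possibly a few more switches from cisplatin to carboplatin. Any subject who switches would drop out of the exploratory platinum subgroup in SAP Section 8.2.4.2, which excludes those treated with both agents. Sample size, visits, eligibility and the SAP text need no change.
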